6.7 Agent Destruction/Disposal

At the completion of the study, there will be a final reconciliation of drug shipped, drug consumed, and drug remaining. This reconciliation will be logged on the drug reconciliation form, signed and dated. Any discrepancies noted will be investigated, resolved, and documented prior to destruction of unused study drug. Drug destroyed on site will be documented in the study files.

7 CLINICAL EVALUATIONS AND PROCEDURES

7.1 Table 1: Schedule and Sequence of Data Collection

Assessment Schedule

	Screening	Baseline/ Randomization		M1 +/- 7 days		M2 +/- 7 days		End of Treatment/M3 +/- 7 days	7 Day Follow Up
		W1	W3	W4	W7	W8	W11	W12	
Informed Consent	X								
Concomitant Medications	X	X		X		X		X	X
Relevant Medical History/Current Medical Condition	X								
Mini-Mental Status Exam, 2 nd Edition (MMSE)	X								
Self-Reported Cognitive	X								

Impairment Since Chemotherapy									
Wechsler Test of Adult Reading (WTAR)		X							
Hopkins Verbal Learning Test, Revised (HVLТ-R): Form 1		X							
Hopkins Verbal Learning Test, Revised (HVLТ-R): Form 2							X		
Controlled Oral Word Association Test (COWA): T1		X							
Controlled Oral Word Association Test (COWA): T2							X		
Color Trails – Part 1 (Form A)		X					X		
Color Trails – Part 2 (Form A)		X					X		
Brief Visuospatial Memory Test – Revised (BVMT-R): Form 1		X							
Brief Visuospatial Memory Test – Revised (BVMT-R): Form 2							X		
Digit Span (subset of WMS-IV)		X					X		
Symbol Digit Modalities Test (SDMT)		X					X		
Rey Complex Figure Copy (Copy Trial Only)		X					X		
Demographic Questionnaire		X							
Godin-Leisure Time Exercise Questionnaire		X					X		
Primary Care Evaluation of Mental Disorders Health Questionnaire (PHQ-9)		X					X		
Fatigue Symptom Inventory (FSI)		X					X		
Patient’s Assessment of Own Functioning Inventory (PAOFI)		X					X		
MRI-Resting state functional MRI and structural MRI.		X					X		
Anthropometric Measurements ¹		X					X		
ECOG	X						X		
2 Day Food Record ²		X		X		X	X		
Hematology (CBC) ³	X			X		X	X		
Blood Chemistry (CMP, PT/PTT, LDL) ⁴	X			X		X	X		

Research Labs (Oxidative stress, Cytokine)	X							X	
Adverse Events				X		X		X	X
Limited Physical Exam	X ⁵							X	
Study Agent/Multivitamin Distribution		X		X		X			
Study Agent Intake & Symptom Logs		X		X		X		X	
Pill Counts				X		X		X	
Follow Up Phone Call									X

¹ Height, Weight, BMI, Waist, & Hip Circumference

² Dietary recall forms and instructions will be distributed in person at the screening visit and collected at the baseline, week 4, week 8, and end of treatment visits

³ Hematology labs do not need to be performed at screening visit if lab results are available within the previous 28 days (+/- 3 days)

⁴ Blood Chemistry labs do not need to be performed at screening visit if lab results are available within the previous 28 days (+/- 3 days)

⁵ The initial limited physical exam can be done at either screening or baseline.

7.2 Evaluations during Screening Visit

7.2.1 All subjects will have the study fully explained to them and will sign an informed consent document prior to having any invasive procedures performed. They will also be assigned an identification number.

7.2.2 Within 6 months of completing chemotherapy, + or – radiation (+/- 7 days), patients will be screened for cognitive impairment. Evidence of cognitive impairment requires each subject answer in the affirmative: ‘do you have problems with memory and attention since having chemotherapy, and do you believe chemotherapy contributed to the problems?’

7.2.3 A limited physical exam will be performed which includes ECOG.
NOTE: The limited physical exam can be done at either screening or baseline.

7.2.4 Concomitant medications, medical history, and current medical condition will be collected.

7.2.5 Mini-Mental State Examination, (MMSE will be administered to screen for and estimate the severity of cognitive impairment in order to determine participant’s eligibility to participate in the study.

7.2.6 Blood will be drawn for CBC, CMP, PT/PTT, and LDL and measurement of plasma antioxidant biomarkers or oxidative stress and inflammation.

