2 OBJECTIVES

2.1 Pilot trial Primary Objectives

- 1. Specific Aim 1: Does nutritional supplementation facilitate cognitive function in adult breast cancer survivors, relative to persons who do not receive this supplementation?** We predict that adult breast cancer survivors receiving nutritional supplementation will experience improved cognitive performance as assessed by a battery of standardized tests of cognitive function. The current pilot study will evaluate the feasibility of administration of the nutritional supplement and placebo in this patient population and performing cognitive function testing at baseline and post supplementation.

2. **Specific Aim 2: Is the facilitation of cognitive function in the nutritional supplementation group mediated by changes in markers of oxidative stress and inflammation, relevant to cognitive performance?** We predict that persons receiving nutritional supplementation will exhibit larger changes in antioxidant markers and that these changes will serve to mediate or explain differences in the cognitive performance of the two groups. The current pilot study will evaluate the feasibility of administration of the nutritional supplement and placebo in this patient population and testing antioxidant levels at baseline and after the supplementation.

3. **Specific Aim 3: Does nutritional supplementation facilitate cognitive function in adult breast cancer survivors, relative to persons who do not receive this supplementation as indicated by changes in structural and resting-state functional markers observed utilizing the MRI/fMRI?** We predict that adult breast cancer survivors receiving nutritional supplementation will experience improved cognitive performance as assessed by a battery of structural and functional changes in imaging markers in the brain. The current pilot study will evaluate the feasibility of administration of the nutritional supplement and placebo in this patient population and performe structural and resting-state functional MRI to evaluate changes in these imaging markers at baseline and after the supplementation.

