4.2 Criteria for exclusion will include: 1) Use of estrogens (oral, dermal or vaginal), progesterone (oral or topical), or androgens during the previous 3 months, 2) Use of over the counter steroid hormonal supplements 3) Patients with advanced or Stage IIIC or IV breast cancer or other cancers. 4) Use of n-3 fatty acids or high dose antioxidant supplements other than what is provided in the trial. 5) History of known allergy to components of the study supplements. 6) Subjects with renal or liver disease (AST/ALT $>$ 5.0 x upper limit of normal as evidenced by impairment of baseline laboratory values); Actual creatinine clearance of $<$ 60 utilizing the Cockcroft-Gault formula (1976), which employs creatinine measurements and a patient's weight to predict the clearance. (The constant for women is 1.04). 7) Concurrent participation in another chemoprevention trial. 8) Evidence of bleeding diathesis or coagulopathy (PTT and/or either PT or INR $>$ 1.5x upper limit of normal (except for subjects receiving anti-coagulation therapy). Concurrent use of Coumadin or Warfarin will be acceptable and monitoring patients on warfarin or Coumadin will follow the standard of care as dictated by the prescribing physician (PT/PTT). If the prescribing physician is not a Moffitt MD, then the prescribing MD

will be notified by the research staff of the subject participating in the study, and monitors for PT, PTT will be obtained from patient during the 3 month study visit for review. 9) Subjects with metabolic abnormalities (e.g. thyroid disorders, insulin dependent diabetes, rheumatologic disease etc.). Subjects with metabolic disorders (a) who are otherwise eligible, (b) treated for hypothyroidism by their primary MD with Synthroid (levothyroxine) and (c) with the approval of the Moffitt treating oncologist will not be excluded from the study. 10) Patients with known claustrophobia, presence of pacemaker and/or ferromagnetic material in their body that would prohibit MRI imaging (ex. tissue expanders). 11) Medical history of concussions 12) Other acute or chronic medical or psychiatric condition or laboratory abnormality that may increase risk associated with study participation or study drug administration, or may interfere with interpretation of study results, and in the judgment of the investigator would make the subject inappropriate for entry into this study.

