Two bottles containing Lovaza and 1 bottle of anthocyanins capsules will be dispensed to all participants upon randomization with adequate number of capsules, to ensure that the subject has sufficient study drug to last until the next planned clinic visit. At baseline and at each monthly visit up to the 3-month final visit, participants will receive these supplements in person to take home with them. At that point, participants will receive instructions regarding how many supplement pills they are to take a day.

Schedule of dose administration of study agents

Arm of Study	Breakfast	Lunch	Dinner
Treatment arm	2 tablets Lovaza 2 tablets Vitablue	2 tablets Vitablue	2 tablets Lovaza 2 tablets Vitablue 1 tablet multivitamin/mineral
Placebo arm	4 tablets matching placebo tablets	2 tablets matching placebo	4 tablets matching placebo tablets 1 tablet multivitamin/mineral

6.3 Contraindications: COGNUTRIN ingredients - n-3 fatty acids may be contraindicated in subjects with bleeding disorders and anthocyanins may be contraindicated in people who are sensitive or allergic to berries.

During study participation, subjects will be instructed to limit their consumption of the following berries to 1 cup per day: blackberry, blueberry, chokeberry, black currant, elderberry, and black raspberry. They will be asked to limit their consumption of the following omega 3's to 2-3 servings (4 oz per serving) a week: walnuts, flaxseed oil, canola oil, fish oils, and fatty fish such as salmon, trout, mackerel, herring, sardines, pilchards, kipper, eel, whitebait, fresh tuna, anchovies, swordfish, bloater, cacha, carp, hilsa, jack fish, katla, orange roughy, and pangas.

6.4 Concomitant Medications: During study participation, subjects will be instructed to suspend consumption of additional supplements containing anthocyanins or omega 3's. Subjects are considered enrolled in the trial from the time that the informed consent document is signed until the time that the subject is off study. All medications (prescription and over-the-counter), taken by the participant while on study will be documented on the concomitant medication CRF and will include: start and stop date, dose and route of administration, and indication.

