In our experience with cancer survivors both clinically and in research studies, over 75-85% of breast cancer survivors use a multivitamin/mineral supplement. Several of these supplements have added ingredients including botanicals and biologics from unknown as well as known sources. The quality, content, standardization techniques, safety as well as stability of the content of these supplements have been a challenge to our team. In order to provide a standard dose to all subjects in the study .ensure safety and prevent any overdosing on other supplements, similar to the content of COGNUTRIN, we have provided a standard multivitamin/mineral to the subjects in our clinical trials with botanicals and biologics.

Our group is currently involved in several active clinical trials where these agents are being used and under IND approval from the FDA. We will keep abreast of the literature in the area of potential drug-drug, drug-nutrient interactions and other contraindications in the evolving research and will amend the study appropriately to ensure subject safety.

The research team has considerable experience with administering cognitive tests to young and older adults and in all cases, participants will be encouraged to do “their best”, which seems to minimize test taking anxiety. Experienced personnel will administer all self-report and cognitive performance measures. The research study staff will carefully monitor participants' reactions and provide information upon request. All participants will be provided with [name] name and telephone number to clarify or answer any questions.

6.6 Adherence/Compliance: During study participation, subjects will be asked to: self-administer the study medication; complete diet recall forms at specified time periods (baseline, 1, 2 and 3 months); avoid consumption of additional nutritional supplements and multivitamins containing the recommended daily allowance (RDA) of Vitamin D. Subjects are expected to: maintain $\geq 85\%$ compliance with study agent intake; comply with dietary, medication and supplement restrictions; and complete the diet recall forms to the best of their ability. Subjects will be interviewed at the monthly scheduled time points, at which time pill counts will be performed to verify compliance with study requirements. Subjects discovered not to be complying with study requirements will have the requirements re-explained to them.

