7.3 Evaluations during Baseline/Randomization Visit

7.3.1 After eligibility has been confirmed based on screening tests using eligibility checklist, subjects will be randomized and supplied with a one-month supply of nutritional supplement (COGNUTRIN) or placebo (n=20/arm) and multivitamin .

7.3.2 Review of completed diet survey and concomitant medications.

7.3.3 Anthropometric measurements will be taken.

- 7.3.4 The following questionnaires will be completed: Godin-Leisure Time Exercise, Patient's Assessment of Own Functioning Inventory (PAOFI); Personal Health Questionnaire (PHQ-9), and Symptoms of Fatigue and Depression (FSI)
- 7.3.5 Cognitive testing will be administered (HVLТ-R: Form 1, COWA: T1, Color Trails Part 1& 2, Digit Span, SDMT, BVMT-R: Form 1, and Rey Complex Figure Copy)
- 7.3.6 Subjects will also undergo a structural and resting-state functional magnetic resonance Imaging (MRI/fMRI)

Subjects should not be randomized until eligibility has been confirmed. All components of eligibility will be confirmed (inclusion criteria and exclusion criteria).

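### The biomarker sample that Aim 2 calls baseline is drawn at screening, apart from the cognitive baseline, with no maximum interval and no defined time off supplements

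*Combined protocol and SAP*

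**What the plan says.** **Timing of the blood.** Section 7.2.6, on the screening visit, reads "Blood will be drawn for CBC, CMP, PT/PTT, and LDL and measurement of plasma antioxidant biomarkers or oxidative stress and inflammation". In Table 1 the row beginning "Research Labs (Oxidative stress, Cytokine" is marked at screening and at end of treatment only. The schema also lists the antioxidant and inflammation samples under screening. Section 7.3, on the Baseline/Randomization visit, includes no blood draw.

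**Timing of everything else.** The cognitive battery ("COWA: T1, Color Trails Part 1& 2, Digit Span, SDMT" and the other tests) is in 7.3.5. MRI, PHQ-9, FSI, PAOFI and anthropometry are at the same visit. The food record is handed out at screening and collected at baseline (Table 1, note 2). No section gives a maximum interval between the two visits.

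**Name and use of the sample.** Specific Aim 2 speaks of "testing antioxidant levels at baseline and after the supplementation". Section 12.5.1 uses biomarker change as the mediator of the group effect on the number of impaired tests. Section 7.7.13 also assigns the inflammatory markers to compliance monitoring and to use as a covariate for cognitive function.

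**Supplements and diet.** Exclusion 4 in 4.2 is "Use of n-3 fatty acids or high dose antioxidant supplements other than what is provided in the trial". It has no look-back, whereas exclusion 1 (hormones) covers the previous 3 months. Section 6.4 says "During study participation, subjects will be instructed to suspend consumption of additional supplements containing anthocyanins or omega 3's", and it dates enrolment from consent: "Subjects are considered enrolled in the trial from the time that the informed consent document is signed until the time that the subject is off" [...]. The 6.3 limits on berries and n-3 foods likewise apply during participation. Section 7.2.1 puts consent before any invasive procedure.

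**The concern.** A mediation analysis needs mediator and outcome measured over the same period. At the end they coincide: blood, cognition and MRI all belong to the 3-month visit. At the start they do not. Biomarker change covers the screening-to-baseline gap plus the intervention, while cognitive change covers the intervention alone. The women are at most about 6 months past treatment, so neither measure need be stable across an unbounded gap.

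The second issue is what the screening sample represents. Consent and blood draw fall at the same visit, so a suspension that begins at consent gives no scheduled time off supplements before the draw, and the food limits have had no time to act. The week-12 sample is taken under both restrictions. A woman who gave up an n-3 or anthocyanin product on entry could show a biomarker change that reflects stopping it (placebo arm) or replacing it (active arm).

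At stake are the within-arm biomarker changes, the precision of the mediator, and the effect sizes that section 3.0 expects a feasibility study to supply.

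**Working it through.** **Step 1. Passages side by side.** The plan states no figure on this point, so there is none to reproduce.

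| Item | Visit | Source |
|---|---|---|
| Consent; suspension and food limits begin | Screening | 7.2.1, 6.3, 6.4 |
| Oxidative-stress and cytokine sample | Screening | Schema, Table 1, 7.2.6 |
| Cognition, MRI, PHQ-9, FSI, PAOFI; food record collected | Baseline/Randomization | Schema, Table 1, 7.3 |
| First dose supplied | Baseline/Randomization | 7.3.1 |
| Second biomarker sample, cognition, MRI | Month 3 | 7.5 |

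The misalignment and the absence of a defined time off supplements follow directly.

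**Step 2. How much residual effects could matter.** Known input: 20 women per arm (schema, 7.3.1). Assumed inputs:
- biomarker SD of 1 at each time and pre/post correlation 0.5 (the value that 12.4 uses as the stability coefficient for the cognitive endpoint);
- true effect 0.5 SD;
- a share p of women carrying over c SD, in the direction of the agent's effect, into the screening sample, gone by week 12;
- carry-over unrelated to arm and to cognitive change.

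The documents do not give p or c. I use p = 10-30% (4-12 of 40 women) and c = 0.5-1.0.

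Formulas:
- Variance of change without carry-over: 1 + 1 - 2 x 0.5 = 1.0.
- Variance added by carry-over: c^2 x p x (1 - p).
- Shift of mean change in each arm: -c x p, which cancels in the difference.
- SE of the between-arm difference: sqrt(2 x V / 20), where V is the total variance of change.
- Multiplier on the biomarker-to-cognition slope: 1 / V.

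| p | c | V | Mean change, active / placebo | Difference | SE | Slope lost |
|---|---|---|---|---|---|---|
| 0 | - | 1.0000 | +0.50 / 0.00 | 0.50 | 0.316 | 0% |
| 10% | 0.5 | 1.0225 | +0.45 / -0.05 | 0.50 | 0.320 | 2% |
| 30% | 0.5 | 1.0525 | +0.35 / -0.15 | 0.50 | 0.324 | 5% |
| 10% | 1.0 | 1.0900 | +0.40 / -0.10 | 0.50 | 0.330 | 8% |
| 30% | 1.0 | 1.2100 | +0.20 / -0.30 | 0.50 | 0.348 | 17% |

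A simulation of 40,000 trials under these assumptions agreed on means and SEs (for example +0.20, -0.30, difference 0.50 and SE 0.346 in the last row).

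**Step 3. Reading the table.** The arm-to-biomarker path is unbiased throughout. The biomarker-to-cognition path is not protected by randomisation, and under these assumptions the indirect effect shrinks in the same proportion, 2-17%. In the last row the standardised biomarker effect falls from 0.50 to 0.50 / sqrt(1.21) = 0.45. A later trial sized on that biomarker effect would need about 21% more women.

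**The case against.** A reader might infer that the sample is taken while women are still using supplements, so that Aim 2's biomarker change contains carry-over. The documents do not support that. Exclusion 4 bars users of n-3 and high-dose antioxidant products. Suspension starts at consent, which precedes the draw. Section 5.2.2 gives anthocyanins a half-life of 4-6 hours and complete excretion within 24 hours, which confines that component to very recent use. No clearance figure is given for n-3, so persistence cannot be shown either way. The 75-85% in section 6.5 refers to multivitamin/mineral products; the remark "Several of these supplements have added ingredients including botanicals and biologics from unknown as well as known sources" does not say how many women take n-3 or anthocyanins. Section 6.4 can be read as letting users enter by stopping, or simply as an on-study rule for everyone.

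A reader might also infer a biased treatment comparison, or within-arm changes that cannot be interpreted at all. Neither follows. Arms are randomised, and even the harshest assumed case moves within-arm means by 0.30 SD.

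Further, 5.8 already collects previous supplement use, and 6.4 records on-study medication, including over-the-counter items, with start and stop dates. The schema ranks biomarkers as other endpoints, and 12.5.1 says its aim is the size of effects rather than significance.

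All of this stands and limits the point. It leaves untouched the separate visits, the unbounded gap, and the lack of any defined time under the supplement and food restrictions before the sample.

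**Conclusion.** The point holds as one of timing and definition. The sample serving as the biomarker baseline is a screening sample, taken at a different visit from the cognitive baseline, with no maximum interval. Residual effects of prior supplements or unrestricted diet cannot be excluded from it, but nothing in the documents shows that they are present. The between-arm biomarker change remains unbiased. The possible loss is distorted within-arm change (0.05 to 0.30 SD in the cases above) and a 2-17% attenuation of the biomarker-to-cognition path. Those sizes rest wholly on the assumed shares, carry-over sizes, correlation of 0.5 and independence from cognitive change. The effect of the different dates alone cannot be sized, because the gap is not given. For an exploratory mediation analysis in a 40-woman pilot this is low-to-moderate priority, worth acting on because the remedy is cheap.

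**What to change.** 1. Move the two research tubes from screening to the Baseline/Randomization visit, before the first dose, and amend the schema, Table 1, 7.2.6 and 7.3 to match. Mediator and outcome then start together, and the sample falls after the 6.3 and 6.4 restrictions have begun. If the tubes stay at screening, state a maximum interval to baseline.
2. Using the supplement history and concomitant-medication dates already collected, report biomarker change with and without women who stopped n-3, anthocyanin or antioxidant products at entry. Products stopped before consent may lack a date; check that the forms capture them.
3. Reconcile exclusion 4 with 6.4, so that it is clear whether a woman who stops a product on entry is eligible. The choice is the sponsor's.

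Cost: a schedule edit and one sensitivity table. Women whose safety bloods are drawn at screening have one extra needle stick; for those with acceptable results on file, the stick only moves. Research tubes are no longer processed for screen failures. The move does not itself guarantee any particular time off supplements, since the screening-to-baseline gap is still unstated. If some women have already been sampled at screening, flag them in the analysis.
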